## **6.4 Statistical Power**

The sample size for our pilot study has been chosen to provide a practical basis for developing variance measures of motivation and engagement in physical activity that will be needed to design a subsequent larger randomized controlled trial. The daily step count was the outcome that this study power calculation was based off of. Since studies have not yet evaluated change in step count in response to an anti-inflammatory strategy in our specific population (older, sedentary adults with depressive symptoms), the variations of change that are gathered from this study will be used to estimate power for large scale efficacy trials. Regardless, we have estimated the standard deviation of change in steps utilizing the variation of steps in older, sedentary adults without depressive symptoms previously published. Assuming SD of change=1045, 80% power, and an alpha=0.05, a sample size of 18/group is required to detect a change of 1000 steps/day. An increase in 1000 steps per day was associated with a 16% reduced risk in all-cause mortality. Thus, to account for attrition, we propose a sample size of 20/group. Additionally with a sample size of 20/group, we will also have 73% power (assuming SD of change=41) to detect a change of 30 min/day of sedentary time. Such a change is noteworthy epidemiological evidence suggests that 30 min/day of sedentary time is associated with 17% increased risk of all-cause mortality in sedentary older adults.

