## CHAPTER 3: RESEARCH DESIGN

### 3.1 Study Objectives and Aims

The overall objective of this study is to gather preliminary evidence on the feasibility and effectiveness of an intervention supplementing fiber and anthocyanins to usual diet compared to control (placebo). We will conduct a 3-month, double-blind randomized, parallel-arm, pilot study in 40 sedentary, older adults with depressive symptoms that is designed to improve inflammation, motivation, and consequent engagement in physical activity. Our specific aims are:

**Aim 1:** Determine the feasibility of an intervention supplementing usual diet with fiber (8 g/day) and anthocyanins (600 mg/day). We hypothesize at least 80% of the participants enrolled will complete the 3-month intervention.

[figure not shown]
**Aim 2:** Gather preliminary evidence on the impact of fiber and anthocyanin supplementation on relevant inflammatory markers. We hypothesize markers relevant to inflammation (interleukin-6, C-reactive protein, and brain-derived neurotrophic factor) tend to reduce after 3 months of fiber and anthocyanin supplementation compared to control.

**Aim 3:** Obtain preliminary evidence on the efficacy of fiber and anthocyanin supplementation to improve the engagement in physical activity, and further determine if this effect is mediated by change in motivation (via Motives for Physical Activities Measure-Revised questionnaire). We hypothesize the physical activity (i.e., average daily step count via accelerometer) tends to increase after 3 months of fiber and anthocyanin supplementation compared to control, and that a substantial portion of this effect is mediated via an increase in motivation.

Our overall hypothesis is that a 3-month dietary intervention supplementing fiber and anthocyanins in sedentary, older adults with depressive symptoms will be feasible and demonstrate preliminary efficacy.

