## 4.2 Recruitment Timeline

Our trial proposes to enroll 40 persons over approximately 6-months. We will recruit for two waves of our intervention. For the first wave of the intervention, we aim to recruit 16 individuals over ~3 months. The 16 individuals will then be randomized to the intervention or control group, and participate in the study for 3 months. During the 3 months the first wave of participants are on the study intervention, we will be recruiting for the second wave (n=24) of the intervention. Once the second cohort of 24 individuals is recruited, they will begin the study intervention as soon as possible. To stay on target, we need to recruit ~7 participants/month. Thus, based on our known research participation rates, and the expected prevalence of depressive symptoms in older adults, we will readily be able to meet our recruitment goal of 40 participants.

There will be two waves of the intervention (n=16 for the first wave, and n=24 for the second wave). For each wave, half of the participants will be randomized to the intervention group and the other half will be in the control group. In an attempt to account for the impact of seasonal variation on physical activity levels, we will employ block (blocks of 4) randomization. For every block of 4 participants, 2 will be randomized to consume the placebo powder and the remaining 2 will be randomized to the blueberry powder.

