## **6.2 Outcome Variables**

Feasibility is defined as participant retention (e.g., the number of participants that complete the intervention out of all participants randomized to an intervention arm), however others will be explored. Feasibility outcomes will be summarized using sample quantities and corresponding 80% confidence interval estimates. The intervention will be considered feasible if at least 80% of the participants randomized, complete the final follow-up.

Relevant inflammatory markers (C-reactive protein, interleukin-6, and brain derived neurotrophic factor) will be measured in blood collected from participants at baseline and final follow-up. Change in inflammatory markers will be calculated. The distribution of change in inflammatory markers will be summarized using sample quantities and kernel density estimates. We will develop 80% confidence interval estimates of inter- and intra-individual variation (i.e., standard deviation) of change in these measures.

Motivation to engage in physical activity will be assessed via self-report questionnaire, Motives for Physical Activities Measure-Revised. Change in motivation will be calculated between baseline and follow-up periods. The distribution of change in motivation scores will be summarized using sample quantities and kernel density estimates. We will develop 80% confidence interval estimates of inter- and intra-individual variation (i.e., standard deviation) of change in these measures.

Engagement in physical activity will be defined as the median daily-step count over 2 weeks prior to each mid-point and/or follow-up visit. We chose the median daily step count, because step counts varies from day to day. Change in median step count will be calculated between the baseline and follow-up. The distribution of change in physical activity will be summarized using sample quantities and kernel density estimates. We will develop 80% confidence interval estimates of inter- and intra-individual variation (i.e., standard deviation) of change in these measures.

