## **6.3 Statistical Methods**

Formal inference and estimation of treatment effects will use a Student's t-test. The mean change (baseline-follow-up) in our outcome variables (inflammatory markers, motivation, step count) in the control group will be compared to the mean change (baseline-follow-up) of the intervention group overtime. A p-value less than 0.05 will be used to determine statistical significance.

The relationship between inflammatory markers, motivation, and engagement in physical activity will be assessed. Given that consistent evidence in populations (including older adults) have shown that supplementation with berries (a source of fiber and anthocyanins) successfully reduces inflammatory markers, we are confident our intervention will successfully lower inflammatory markers. Thus, we will evaluate the relationship between of change in inflammatory markers with change of physical activity utilizing a linear regression.

To determine if change in motivation is on the pathway between change in inflammation and engagement in physical activity, we will use linear regression with and without the addition of change in motivation to the model. If adjusting for change in motivation changes the estimate by >10%, then motivation will be considered a part of the causal pathway. A p-value less than 0.05 will be used to determine statistical significance.

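### Section 6.4 states 73% power for sedentary time where a two-sided test gives about 62%, and its 80% power for step count rests on an unstated attrition rate of about 10%

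*Combined protocol and SAP*

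**What the plan says.** Section 6.4 gives two power statements in one paragraph.

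- **Step count (primary outcome):** "Assuming SD of change=1045, 80% power, and an alpha=0.05, a sample size of 18/group is required to detect a change of 1000 steps/day". The allowance for dropout follows: "Thus, to account for attrition, we propose a sample size of 20/group". No attrition rate is given.
- **Sedentary time:** 73% power at 20 per group for a change of 30 min/day, assuming an SD of change of 41.

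Neither statement says whether alpha is one-sided or two-sided. Section 6.3 names the test ("Formal inference and estimation of treatment effects will use a Student's t-test") and the threshold ("A p-value less than 0.05 will be used to determine statistical significance"), again without sidedness.

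The protocol's only numerical retention figure is 80%. Aim 1 in section 3.1 says "We hypothesize at least 80% of the participants enrolled will complete the 3-month intervention", and section 6.2 makes it the decision rule: "The intervention will be considered feasible if at least 80% of the participants randomized, complete the final follow-up". Section 6.1 plans intention-to-treat and per-protocol analyses, but no section describes how missing follow-up values are handled.

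**The concern.** There are two separate issues.

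First, the two power figures in section 6.4 do not appear to use the same test. A reader would assume one alpha of 0.05 applied in one way throughout the paragraph. If it is two-sided, as the step-count figure implies, the sedentary-time power is overstated by about 11 percentage points, and power that is already below the usual 80% looks better than it is.

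Second, the step-count power is presented as protected against attrition, but the size of that protection is left for the reader to work out. It is smaller than the loss the plan would accept and still call the intervention feasible. Without a missing-data method, a participant with no follow-up step count contributes no change score to the t-test, so completers set the power.

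Both figures affect how a non-significant result is read, and they may be carried into planning of the later trial.

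**Working it through.** **Inputs**

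- Step count: difference 1000, SD of change 1045, alpha 0.05, power 80% (section 6.4).
- Sedentary time: difference 30 min/day, SD of change 41, 20 per group (section 6.4).
- Allocation 1:1, from blocks of four (section 4.2).
- Two-sample Student's t-test on change (section 6.3).
- Retention floor 80% (sections 3.1 and 6.2).
- Assumption: the sidedness of alpha is not stated, so both versions are tried.

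**Step 1. Reproduce 18 per group**

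Normal approximation: n per group = 2 × [SD × (z for alpha + z for power) / difference]².

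- Two-sided: 2 × [1.045 × (1.960 + 0.842)]² = 17.1, rounded up to 18. This matches the plan.
- One-sided: 2 × [1.045 × (1.645 + 0.842)]² = 13.5, rounded up to 14. This does not match.

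The exact (noncentral t) calculation gives 18.15 two-sided and 14.2 one-sided. The step-count calculation is therefore two-sided.

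**Step 2. Try to reproduce 73% for sedentary time**

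Standardised difference d = 30/41 = 0.732. With n = 20 per group, the noncentrality is d × √(n/2) = 0.732 × √10 = 2.314, on 38 degrees of freedom.

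| Test at 20 per group | Critical value | Power |
|---|---|---|
| t, two-sided | 2.024 | 61.6% |
| Normal approximation, two-sided | 1.960 | 63.8% |
| t, one-sided | 1.686 | 73.5% |
| Normal approximation, one-sided | 1.645 | 74.8% |

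Only the one-sided t-test gives the stated 73%. Rounding of the inputs does not explain the gap. Two-sided power of 73% at 20 per group needs d of about 0.835, which means an SD of 30/0.835 = 35.9 rather than 41.

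**Step 3. The attrition allowance**

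- Implied by the plan: (20 − 18)/20 = 10%. Equivalently, 18/0.90 = 20.
- Accepted as feasible: 20% of 40 = 8 lost, leaving 32, or 16 per group if losses are balanced.

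**Step 4. Two-sided power by number of completers**

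For step count, d = 1000/1045 = 0.957.

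| Completers per group | Retention | Step count, t | Step count, normal | Sedentary time, t |
|---|---|---|---|---|
| 20 | 100% | 83.9% | 85.7% | 61.6% |
| 18 | 90% | 79.6% | 81.9% | 56.9% |
| 16 | 80% | 74.5% | 77.2% | 51.7% |

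Unequal losses with 32 completers change little: 74.4% at 15/17 and 73.9% at 14/18. At 16 per group, the step-count difference detectable with 80% power (two-sided t) is about 1,070 steps/day.

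**The case against.** **On attrition.** The strongest reply is that 80% is a success floor, not a forecast. Both places that use it say at least 80%. Planning for a 10% loss while tolerating up to 20% is not a contradiction, and section 8.2 reports high retention in similar work at the institute. This stands. A reader might infer that the trial is expected to run at 74% power, or that the sample size contradicts the feasibility rule. The documents support neither. The 74.5% belongs to the boundary only. If true retention were exactly 80%, trials that meet the criterion would average about 76.5% power; at 85% the average is about 77.7%, and at 90% about 79.5% (binomial dropout at 20 per arm, t-test power averaged over outcomes with at least 32 completers).

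Part of the shortfall is also method. The plan's 18 matches the normal approximation, under which the floor gives 77.2%.

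**On importance.** Section 6.4 says the size was chosen mainly to obtain variance estimates for a larger trial, and admits that the SD comes from adults without depressive symptoms. A five-point change in power is small beside that uncertainty. This also stands, and it is why no increase in sample size is argued for. It does not excuse leaving the assumption unstated, because section 6.3 still plans formal testing at 0.05 on the outcome that was powered.

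**On sedentary time.** It could be said that the text openly gives the figure at 20 per group, so the lack of a dropout allowance is visible, and that a one-sided test is never ruled out. The first part is fair. The second does not rescue the figure, since a one-sided alpha would give 14 or 15 per group for step count rather than the stated 18. One sidedness cannot produce both numbers.

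**Conclusion.** The sedentary-time power in section 6.4 is wrong as written if alpha is two-sided, which is the only reading that yields the plan's 18 per group. It should be about 62% (64% by normal approximation), not 73%, before any dropout. With dropout it is about 57% at 18 and 52% at 16 completers per group.

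The step-count statement is not miscalculated. "a sample size of 18/group is required to detect a change of 1000 steps/day" reproduces, and 20 per group is consistent with a 10% loss. The defect is that the 80% power depends on about 90% retention, a condition the plan does not state and that is stricter than its own feasibility floor. At the floor the power is about 74.5% (77% by normal approximation).

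These results rest on the plan's own SDs and differences, 1:1 allocation, roughly balanced losses, and an analysis of participants with follow-up data.

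**What to change.** Keep 40 participants and restate section 6.4:

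1. Name alpha as two-sided 0.05 for both calculations, and repeat this in section 6.3.
2. Replace the 73% for sedentary time with about 62% at 20 per group, adding about 57% at 18 and 52% at 16 completers per group.
3. State that the 80% power for 1000 steps/day assumes about 10% attrition, and that at the 80% retention floor it falls to about 74–75%, with a detectable difference of about 1,070 steps/day.

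The cost is wording only; design, sample size and analysis do not change. The stated power becomes less favourable, modestly for step count and more so for sedentary time. For reference, holding 18 completers per group at 20% loss would need 18/0.80 = 22.5, so 23 per group (46 in total). The pilot's stated purpose does not require that.

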### 3.5 Study Endpoints

Primary Outcomes – The primary outcome for this study will be engagement in physical activity.

1. **Engagement in Physical Activity:** Engagement in physical activity will be evaluated by the median # of steps per/day (via ActiGraph) of the previous two weeks before each visit (e.g., 2 weeks before baseline or 2 weeks before follow-up). We will also evaluate median sedentary minutes/day of the previous two weeks before visits.

Secondary Outcomes – We will evaluate several secondary outcomes including:

1. **Feasibility** : Feasibility will be defined as participant retention rate (i.e., number of participants that complete the intervention/total randomized).
2. **Inflammatory Biomarkers:** Serum markers relevant to inflammation, (serum brain-derived neurotrophic factor, BDNF; C-reactive protein, CRP; interleukin-6, IL-6) at baseline and follow-up will be measured by Quest Diagnostics or our collaborators at the University of Connecticut Metabolic Phenotyping Lab.
3. **Motivation:** Motivation to engage in physical activity (our proposed mediator between inflammation and physical inactivity) will be assessed by the self-report questionnaire Motives for Physical Activities Measure-Revised that has been used in middle-aged and older adults.

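### The 73% power quoted for sedentary time does not follow from its printed inputs on the two-sided 0.05 basis that yields 18/group for steps; that basis gives about 62%

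*Combined protocol and SAP*

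**What the plan says.** Section 6.4 makes two power statements in one paragraph.

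- **Step count, the basis of the sample size:** "Assuming SD of change=1045, 80% power, and an alpha=0.05, a sample size of 18/group is required to detect a change of 1000 steps/day". This is then raised to 20/group for attrition; no dropout rate is given.
- **Sedentary time, at 20/group:** "we will also have 73% power (assuming SD of change=41) to detect a change of 30 min/day of sedentary time". No alpha, sidedness or method is printed with this second statement.

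Section 6.3 names the test: "Formal inference and estimation of treatment effects will use a Student's t-test". It sets the threshold: "A p-value less than 0.05 will be used to determine statistical significance". It then lists what is compared between arms: "The mean change (baseline-follow-up) in our outcome variables (inflammatory markers, motivation, step count) in the control group will be compared". Sedentary time is not in that list, although section 3.5 says of it: "We will also evaluate median sedentary minutes/day of the previous two weeks before visits".

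Neither section says whether testing is one-sided or two-sided.

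**The concern.** Two power figures in one paragraph, for the same two-arm comparison, should come from the same test at the same level. Here no single choice of sidedness gives both. The step-count figure fits a two-sided test. The sedentary-time figure is too high for a two-sided test and fits only a one-sided one.

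What is at stake is how a null result on sedentary time would be read. The plan justifies the 30 min/day difference by a mortality association, so readers will take the quoted power as the trial's chance of seeing a difference that matters. At 73% they would put the risk of missing it at 27%. On the printed inputs, tested two-sided, it is about 38%.

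The power figure also belongs to a comparison that section 6.3 does not list.

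**Working it through.** **Inputs**

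| Quantity | Steps | Sedentary time | Source |
|---|---|---|---|
| Difference between arms | 1000 steps/day | 30 min/day | 6.4 |
| SD of change | 1045 | 41 | 6.4 |
| n per group | 18 | 20 | 6.4 |
| Stated power | 80% | 73% | 6.4 |
| Alpha | 0.05 | 0.05, carried over (assumption) | 6.4; 6.3 threshold |
| Test | two-sample t on change | same | 6.3 |
| Allocation | 1:1 | 1:1 | 4.2 |

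**Formulas.** Let d = difference/SD.

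- Normal approximation: n per group = 2(z_α + z_β)²/d², and power = Φ(d√(n/2) − z_α). Here z_α is 1.960 two-sided or 1.645 one-sided, and z_β = 0.842 for 80% power.
- t-test: noncentral t with 2n − 2 degrees of freedom and noncentrality d√(n/2).

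**Step 1: reproduce the step-count figure to identify the basis.** d = 1000/1045 = 0.957.

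- Two-sided, normal: 2(1.960 + 0.842)²/0.957² = 17.1, rounded up to 18. This matches the plan.
- Two-sided, t-test: n = 18.15; power at 18/group is 79.6% and at 19/group 81.9%. This matches to rounding.
- One-sided, normal: 2(1.645 + 0.842)²/0.957² = 13.5, rounded up to 14.
- One-sided, t-test: n = 14.2, so 15/group. Power at 18/group would be 87.9%.

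The printed 18/group therefore comes from a two-sided calculation.

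**Step 2: apply that basis to sedentary time.** d = 30/41 = 0.732; noncentrality = 0.732 × √10 = 2.314.

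| Test at 20/group | Normal | t-test |
|---|---|---|
| Two-sided 0.05 | Φ(2.314 − 1.960) = 63.8% | 61.6% |
| One-sided 0.05 | Φ(2.314 − 1.645) = 74.8% | 73.5% |
| Stated | 73% | 73% |

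The two-sided values fall 9 to 11 points short of 73%.

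**Step 3: look for another explanation.**

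- *Rounding of the SD.* SDs from 40.5 to 41.5 give 62.7% to 60.6%, so rounding does not explain it.
- *A paired or one-sample t-test with n = 20.* This gives 87.4%, so it does not match either.
- *A misprinted input.* Two-sided 73% at 20/group would need an SD of about 35.9 or a difference of about 34.2 min/day. The documents cannot settle this.
- *A larger sample.* With the printed SD and difference, two-sided 73% needs about 26/group (73.5%).

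**Step 4: what the design delivers two-sided.** At 20/group, the difference detectable with 80% power is about 37 min/day. If only 18/group are analysed, power for 30 min/day is 56.9%. The 18 is an assumption, because the plan states no number of completers.

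**The case against.** The strongest reply is that the sedentary-time sentence prints neither alpha nor sidedness, and that a one-sided 0.05 t-test on its own inputs gives 73.5%. The number can therefore be reproduced. On this view what is shown is an undeclared and inconsistent basis rather than a false figure, and two-sided is only inferred from the step-count sentence.

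Part of this stands. The two-sided basis is an inference, and so is carrying alpha 0.05 over to the second statement. But the reply does not rescue the figure. No one-sided test is declared anywhere. Applied throughout, it would undo the 18/group; applied to sedentary time alone, it would change the basis mid-paragraph without notice. A reader who uses the basis that yields 18/group gets 62% to 64%.

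Three smaller objections have some force.

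- Rounding up to exactly 18 comes from the normal approximation, which gives 63.8%. The planned test is a t-test, so 61.6% is the better figure to print; the gap to 73% remains under both.
- Section 6.3 opens with a general statement that treatment effects are tested by t-test, and section 3.5 places sedentary minutes under physical activity. The test can be inferred, so the gap is the omission from the list of compared outcomes.
- 18/group is only one guess at completers. The plan's own 80% retention threshold would mean 0.80 × 20 = 16/group, where two-sided power is 51.7%.

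This is also a pilot, sized mainly to estimate variation. That limits the consequence but does not make the printed power correct.

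**Conclusion.** The concern holds. On the two-sided 0.05 basis that reproduces 18/group for steps, the printed sedentary-time inputs give 61.6% power by t-test (63.8% by normal approximation), not 73%. The overstatement is about 11 percentage points.

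This rests on three assumptions: alpha 0.05 applies to both statements, the SD of 41 and the difference of 30 min/day are printed correctly, and all 20 per group are analysed. A one-sided calculation is the closest numerical match to 73%, but the documents do not show that it was the cause.

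The effect is confined to a supplementary measure. Enrolment and the step-count sample size do not change. Nor does the sizing of the later trial, which section 6.4 bases on the variation of change observed here. It should be fixed, but nothing else in the design depends on it.

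**What to change.** 1. Check the SD of 41 and the difference of 30 min/day against the original calculation.
2. If both stand, replace the 73% in section 6.4 with: *about 62% power (two-sided alpha 0.05, 20/group analysed; about 57% if 18/group are analysed)*. Label the 18/group figure as an assumption about completers.
3. If an input was misprinted, correct it and recompute the power two-sided.
4. State that both calculations in section 6.4 and the t-test in section 6.3 are two-sided. Settling this before analysis also rules out a later choice between one-sided and two-sided p-values.
5. Add sedentary minutes/day to the outcomes listed for the t-test in section 6.3, so that the power figure refers to a planned comparison.

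The cost is one corrected sentence in section 6.4 and a few words in section 6.3. The quoted power becomes less favourable, and one supplementary comparison becomes explicit. Enrolment and the step-count rationale stay as they are.
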